6.3. Administration of Test Articles

The study lenses will be those prescribed by the investigator and purchased by the subject.

6.4. Packaging and Labeling

The test products will be packaged in sterile blister packs as the primary packaging. A sample Test lens label and packaging are shown below:

6.5. Storage Conditions

Any test lenses stored at the clinical site should be maintained at ambient temperatures and out of direct sunlight.

6.6. Collection and Storage of Samples

No samples will be collected as part of the study procedures.

6.7. Accountability of Test Articles

Not applicable.

7. STUDY EVALUATIONS

7.1. Time and Event Schedule

Table 2: Time and Events

Visit Information	Visit 1 Registration	2-Week Questionnaire	4-Month Questionnaire	12-Month Questionnaire
Time Point	Day 0	Day 10-30	Day 110-150	Day 345-395
Statement of Informed Consent	X			
Inclusion / Exclusion Criteria	X			
Contact Information	X			
ECP Registration Questionnaire	X			
Patient Registration Questionnaire	X			
Reminder		X	X	X
2-Week Questionnaire		X		
4-Month Questionnaire			X	
12-Month Questionnaire				X
ECP Adverse Event Form (paper CRF)		As Needed	As Needed	As Needed

7.2. Detailed Study Procedures

Prior to Visit 1, the registrant is fitted with the Test or Control lens, and purchases a supply of lenses.

VISIT 1

Visit 1: Registration		
Step	Procedure	Details
1.1	Study Explained	Recruiting Practitioner or Staff explains participation in Registry
1.2	Statement of Informed Consent	Registrant completes Informed Consent (IC) Note: The subject must be provided with a signed copy of this document.
1.3	Demographics	Record the subject's year of birth, age and gender
1.4	ECP Registration Questionnaire (ERQ)	The Eye Care Practitioner (ECP) completes a paper ECP Registration Questionnaire (ERQ) for each Registrant recording the following information (steps below) as source documentation.
1.5	Iris Color	The investigator will record the subject's iris color based on the 15-color scale provided (Appendix C).
1.6	Contact Lens History	Experienced CL wearer (Yes/No) If Yes, number of years total, last CL brand, replacement frequency, and when last used.
1.7	Contact Lens Details (New lenses)	Brand (full name), base curve, powers, recommended replacement period, recommended care system, and planned usage (Full/Part-Time). If part-time, number of days/week.
1.8	Reason for Lens Selection	Up to three reasons for selection of lens type to be indicated by the ECP investigator.
1.9	Eligibility after Screening	All responses to Screening Inclusion Criteria questions must be answered "Yes" and all responses to Exclusion Criteria must be answered "No" for the subject to be considered eligible.
1.10	Patient Registration Questionnaire (PRQ)	Registrants complete the Patient Registration Questionnaire. When possible, the PRQ should be completed on the same day as the ERQ. Please refer to [REDACTED] attached to this protocol (Appendix D)
1.11	Contact Details	Subject provides contact details to CRO by texting study ID number and email address to the dedicated Kiosk Set-Up texting line that will be provided to them by the site.

Visit 1: Registration		
Step	Procedure	Details
1.12	Kiosk Set-up	On receiving, the subjects contact details, subjects Kiosk will be set up and reminders will send to subjects.

2-Week Questionnaire		
Step	Procedure	Details
2.1.	Reminder	Registrant receives an email reminder and link to online follow-up questionnaire (Kiosk). In cases where a subject fails to respond to the email prompts, at least two additional emails will be sent, approximately 1 week apart. As a final resort a text message may be sent with a similar prompt.
2.2.	2-Week Questionnaire	2-Week Questionnaire is completed online by Registrant.
2.3.	Remuneration	Payment for Registration and 2-Week Questionnaire is arranged (electronic voucher).
2.4.	Adverse Events	Follow-up on Events reported at 2-Week Questionnaire are completed by the Recruiting Practitioner/PI.

4-Month Questionnaire		
Step	Procedure	Details
3.1.	Reminder	Registrant receives an email reminder and link to online follow-up questionnaire (Kiosk). In cases where a subject fails to respond to the email prompts, at least two additional emails will be sent. As a final resort a text message may be sent with a similar prompt.
3.2.	4-Month Questionnaire	4-Month Questionnaire is completed online similar to 2-week Questionnaire for Registrant.
3.3.	Remuneration	Payment for 4-Month Questionnaire is arranged (electronic voucher).
3.4.	Adverse Events	Follow-up on Events reported at 4-Month Questionnaire are completed by the Recruiting Practitioner/PI.

12-Month Questionnaire		
Step	Procedure	Details
4.1.	Reminder	Registrant receives an email reminder and link to online follow-up questionnaire (Kiosk) In cases where a subject fails to respond to the email prompts, at least two additional emails will be sent. As a final resort a text message may be sent with a similar prompt.
4.2.	12-Month Questionnaire	12-Month Questionnaire is completed online similar to the previous follow-up questionnaires for Registrant.
4.3.	Remuneration	Payment for completing the 12-Month Questionnaire is arranged (electronic voucher).
4.4.	Adverse Events	Follow-up on Events reported at 12-Month Questionnaire are completed by the Recruiting Practitioner/PI.
4.5.	Final Form	Indicate if the subject completed the study successfully. If subject discontinued from the study, indicate the reason.

7.3. Unscheduled Visits

Since there are no scheduled follow-up visits, unscheduled visits are not applicable. Registrant will attend aftercare visits in the normal course of routine care.

7.4. Laboratory Procedures

Not applicable

8. SUBJECTS COMPLETION/WITHDRAWAL

8.1. Completion Criteria

Subjects are considered to have completed the study if they:

- Provided informed consent
- Are eligible
- Completed at least two follow-up questionnaires including the 12-month Questionnaire.

8.2. Withdrawal/Discontinuation from the Study

A subject will be withdrawn from the study for any of the following reasons:

- Subject withdrawal of consent

- Subject not compliant to protocol
- Subject lost to follow-up, i.e. misses two consecutive follow-up questionnaires.
- Subject death during the study period
- Subject develops significant or serious adverse events causing discontinuation of study lens wear
- Investigator's clinical judgment regarding for subject safety reasons (that it is in the subject's best interest to stop contact lens use)

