2.2. Endpoints

All of the primary and secondary endpoints will be assessed using the follow-up questionnaire administered at 2-weeks, 4-months and 12-months after the enrollment visit (Visit 1).

Primary endpoints

Vision Satisfaction in Bright Lighting

Subjects will be asked to evaluate their vision satisfaction in bright lighting by rating their level of agreement with the statement “I was satisfied with the quality of my vision in bright lighting with these contact lenses” using a 5-point agreement Likert scale (1: Strongly Disagree, 2: Disagree, 3: Neither Agree nor Disagree, 4: Agree and 5: Strongly Agree).

Secondary endpoints

Overall quality of vision

This will be assessed subjectively using the item “I am satisfied with the overall quality of my vision with these contact lenses”. The item uses a 5-point agreement scale (1: Strongly Disagree to 5: Strongly Agree)

Pulfrich Effect

This will be assessed subjectively using the item “While wearing these lenses, my depth perception of moving objects has NOT been impacted”. Subjects who disagree or strongly disagree with the statement will be considered to have experienced the Pulfrich effect.

Overall comfort

This will be assessed using the item “How would you rate the overall comfort of these contact lenses?”. The item uses the 5-point satisfaction scale, 1: Excellent, 2: Very Good, 3: Good, 4: Fair and 5: Poor.

Reported serious and significant ocular adverse events:

Incidence rate serious and significant ocular adverse events during the study period will be calculated (in 100 patient-year) using all available data from the entire study.

Other endpoint(s):

1. Overall satisfaction
2. Cosmetic appearance assessment
3. Lens storage compliance
4. Reasons for discontinuations
5. All reported ocular and non-ocular adverse events
6. Other subjective assessments (indoor performance, overall opinion, average wear time, etc.)

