4.2. Study Design Rationale

The study is designed as an observational, prospective, non-interventional, multi-center, multi-national post-market study to evaluate the effectiveness of ACUVUE® OASYS with Transitions™ over a period of one year in the general population of spherical contact lens wearers and under general clinical practice. By allowing wide subject eligibility criteria, wide age range and different clinical practices from different countries, the study is ideal for obtaining real world data to assesses the effectiveness of this new technology.

This a non-randomized study and the sponsor has no control of the treatment assignment. The Test and Control groups may have large differences on their baseline characteristics, and these differences can lead to biased estimates of treatment effects. Appropriate statistical methods will be used to reduce the bias (see Section 14 for more details).

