14.3. Analysis Populations

Per-Protocol Population:

All eligible subjects who have completed at least two follow-up questionnaires including the 12-month questionnaire and did not substantially deviate from the protocol as determined by the trial cohort review committee prior to database hard lock (Per-Protocol Population). Justification of excluding subjects with protocol deviations in the per-protocol population set will be documented in a memo to file.

Full Analysis Population:

All enrolled subjects (signed consent form) regardless of subsequent withdrawal from study or deviation from protocol. At least one observation should be recorded.

Both primary and secondary analysis will be conducted on full analysis set. A sensitivity analysis will be conducted on the per-protocol population. To evaluate the impact of missing data, sensitivity analysis will be conducted using multiple imputation.

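### Section 8.2 makes non-compliance an automatic reason for withdrawal from the study, which ends the collection of later ratings and adverse event reports in a registry meant to describe real-world use

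*Combined protocol and SAP*

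**What the plan says.** Section 8.2 opens its list with "A subject will be withdrawn from the study for any of the following reasons". The second item is "Subject not compliant to protocol". The item is not defined, has no severity threshold and names no decision-maker. The section does not say whether questionnaires go on after withdrawal. Missing two consecutive questionnaires is a separate item in the same list.

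Section 14.3 defines the full analysis population as "All enrolled subjects (signed consent form) regardless of subsequent withdrawal from study or deviation from protocol", and adds "At least one observation should be recorded". The primary and secondary analyses use this set. The per-protocol population is limited to subjects with at least two follow-up questionnaires, including the 12-month one, who "did not substantially deviate from the protocol as determined by the trial cohort review committee prior to database hard lock". Section 10 has deviations reported, tracked and corrected, and does not mention withdrawal.

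After Visit 1, Table 2 schedules only the 2-week, 4-month and 12-month questionnaires, and Section 7.3 confirms that there are no scheduled follow-up visits. Under Section 13, investigators do not report events automatically; a questionnaire item about eye problems starts the process. Section 14.9 does not impute in the main analysis and adds multiple imputation as a sensitivity analysis.

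On purpose, Section 4.2 says that "the study is ideal for obtaining real world data to assesses the effectiveness of this new technology". Section 2.2 lists "Lens storage compliance" among the other endpoints.

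**The concern.** In a registry with no follow-up visits, withdrawal from the study in the ordinary sense means that the questionnaires stop. Two things are then lost for a subject judged non-compliant: the later ratings that feed the primary odds ratio over three periods, and the question through which a serious or significant ocular event would come to light. The subject is selected by behaviour, so the loss need not be unrelated to satisfaction or to event risk. Because the lens is known to everyone (Section 5.2) and the criterion is undefined, the rule could also be applied unevenly between arms.

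At stake is how far the full-analysis result describes all wearers followed for a year, as the stated aim requires, and whether the event rate covers the wearers who did not follow the protocol.

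**Working it through.** **1. The passages side by side**

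| Section | What happens to a subject who departs from the protocol |
|---|---|
| 8.2 | Withdrawn from the study if non-compliant (mandatory, undefined) |
| 10 | Deviation reported, tracked and corrected; no withdrawal |
| 14.3, full analysis set | Subject kept, with at least one observation |
| 14.3, per-protocol set | Substantial deviators removed by a committee before hard lock |

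The per-protocol step acts on subjects who answered at 12 months, so it presupposes deviators who were followed to the end. Only Section 8.2 acts during follow-up. If it is applied after the 2-week questionnaire, the subject has one rating of three.

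**2. Adverse events**

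Section 14.6 divides the number of subjects with an event by total exposure in years, with exposure censored at dropout. A withdrawn subject adds neither events nor time afterwards. The rate is undistorted only if the later event rate in these subjects equals that in the rest.

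**3. The plan's own figures**

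- Enrolment (Section 14.2): 240/(1 − 0.20) = 300 per arm. Reproduced.
- Table 4, 0.77 versus 0.86, ρ = 0.5, two-sided α 0.05, power 80%, n = 3. Here p̄ = 0.815, √(2p̄q̄) = 0.5491 and √(p_C q_C + p_T q_T) = 0.5454, so N = (1.960 × 0.5491 + 0.8416 × 0.5454)² × (1 + 2 × 0.5)/(3 × 0.09²) = 194. Table 4 states 194.
- Two other cells in that row do not reproduce (ρ = 0.3: 156 against 145; ρ = 0.7: 233 against 242). They are not used here and do not affect this point.

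**4. Loss of power (illustration)**

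The documents give no non-compliance rate. Assume that 5% to 20% of 300 per arm are withdrawn after one or two ratings, with compound symmetry and ρ from 0.3 to 0.7. A subject with k ratings carries information k/(1 + (k − 1)ρ). With w withdrawn after k ratings:

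effective N = 300 × [(1 − w) + w × I(k)/I(3)]

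For w = 0.20, k = 1, ρ = 0.5: I(1)/I(3) = 1/1.5 = 0.667, so effective N = 300 × (0.80 + 0.20 × 0.667) = 280.

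Power = Φ{[0.09 × √(3N/(1 + 2ρ)) − 1.960 × 0.5491]/0.5454}

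- N = 300: Φ(1.53) = 93.7%
- N = 280: Φ(1.41) = 92.0%

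Over the whole grid effective N runs from 272 to 299, and the largest loss is this 1.7 points. If the same fractions are taken from 240 instead of 300, the largest loss is 2.4 points (93.7% to 91.3% at ρ = 0.3) and the lowest power is 79.6% (ρ = 0.7).

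**5. Possible bias (illustration)**

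If a fraction w of an arm is non-compliant, with satisfaction s_n against s_c in the rest, removing them shifts that arm's later-period proportion by w(s_c − s_n).

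- 10%, 80% against 60%: 0.80 − (0.90 × 0.80 + 0.10 × 0.60) = 0.020, or 2.0 points.
- 5%, 80% against 70%: 0.5 points. 15%, 80% against 50%: 4.5 points.
- With the 2-week rating retained, a simple average of the 2.0-point case over three periods is (0 + 2.0 + 2.0)/3 = 1.3 points.
- Same shift in both arms: 2.0 − 2.0 = 0 in the difference.
- Non-compliant wearers more satisfied than the rest: the sign reverses.

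All these inputs are assumptions. They show that bias is possible but do not fix its size or sign.

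**The case against.** A reader might infer that Sections 8.2 and 14.3 contradict each other, so that the full analysis set cannot hold the data it claims to hold. The text does not support this. Section 14.3 keeps subjects "regardless of subsequent withdrawal from study or deviation from protocol" and asks for one observation; it promises no ratings after withdrawal. Ratings given earlier stay in, and so do deviators who are not judged non-compliant, since no passage equates the two terms.

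A reader might also infer that the rule strips out real-world lens behaviour. That goes too far. Test lens replacement may follow the practitioner's advice, any marketed care product is allowed, and storage compliance is measured as an outcome. Non-compliance may mean mainly study procedures. Against this, the protocol does specify bilateral daily wear of the Test lens and, for Control, daily wear with 2-weekly or monthly replacement. The most obvious procedural failure, missed questionnaires, already has its own item. The text leaves the meaning open.

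Nor do the documents show that whoever decides on withdrawal has seen earlier satisfaction ratings. Subjects enter these online, and the practitioner is brought in when an eye problem is reported.

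Some protection exists. Withdrawals are within the allowance from 300 to 240, dropout above 20% raises enrolment, reasons for dropout are monitored, and multiple imputation is planned. Replacement restores numbers, not the missing ratings. The imputation has no stated provision for withdrawal triggered by behaviour, and Section 14.9 rests on past trials giving no evidence of systematic dropout. These protections reduce the point without removing it.

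**Conclusion.** The point holds as a design weakness worth correcting. As written, the rule is mandatory and undefined. Where it is applied, it ends later ratings and event capture for a behaviour-selected group, while the rest of the plan deals with deviations by tracking and by per-protocol exclusion. This rests on one reading, that withdrawal from the study stops the questionnaires; Section 8.2 does not say otherwise.

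The effect on power is minor: at most 1.7 points from 300 per arm in the scenarios examined. The bias in the primary odds ratio and in the event rate cannot be sized or signed from the documents, and it would largely cancel in the comparison if non-compliance and its link with satisfaction were similar in both arms. A fixed bias, such as 2.0 points set against the 9.5-point difference in Table 3 (86.6% − 77.1%), should not be claimed. It would need assumed rates and concentration in one arm, and it compares a later-period shift with 2-week data. The case for change is that the loss is avoidable and may be informative.

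**What to change.** In Section 8.2, remove non-compliance as a reason for withdrawal from the study, or state that it does not end follow-up. Then:

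- record the deviation under Section 10;
- continue the scheduled questionnaires and event capture unless the subject withdraws consent;
- keep all ratings and events in the full analysis set;
- use deviations only to decide per-protocol membership under Section 14.3.

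The change concerns data collection only and has no bearing on whether a subject goes on wearing the lenses.

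The cost is a short protocol amendment, carried into the stand-alone SAP. The questionnaires and reminders are already scheduled. The small downside is that some retained ratings will come from subjects who deviated, which the planned per-protocol sensitivity analysis already addresses.

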4. STUDY DESIGN AND RATIONALE

4.1. Description of Study Design

This registry study is a one-year, one-visit, observational, prospective, open-label, two-arm, multi-center, multi-national, post-market study. Approximately 300 patients who have recently been fitted with the ACUVUE® OASYS with Transitions™ (Test) and approximately 300 patients who have recently been fitted with spherical non-photochromic reusable marketed silicone hydrogel contact lenses (of any brand) (Control) will be enrolled in the study, a total of 600 subjects. The goal is for a sample size of 480 subjects (~240/arm) after subjects who withdraw or are lost-to-follow-up.

At Visit 1, each subject will be first consented to participate in the study. The ECP will then complete the paper ECP Registration Questionnaire (ERQ) for the given consented subject and collect his/her demographics and baseline information. Participants who meet eligibility criteria, will be asked to complete the Patient Registration Questionnaire (PRQ). At the end of the visit, registrants will be instructed to complete the survey follow-up questionnaire online at 2-weeks (day 10-30), 4-months (day 110-150) and 12-months (day 345-395) from Visit 1

(day 0). The registrants will receive an email reminder and link to the online questionnaire (Kiosk) prior to each evaluation period. Follow-up on events reported at each evaluation period will be completed by the Recruiting Practitioner/PI.

Country specific Good Clinical Practice (GCP) standards, laws, and applicable regulations were reviewed in designing the clinical study protocol to ensure compliance in the management of the clinical trial and to protect the rights and interest of subjects.

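### The lost-to-follow-up rule in Section 8.2 withdraws subjects who missed the first two questionnaires before the 12-month questionnaire opens, and the plan provides for no data collection after withdrawal

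*Combined protocol and SAP*

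**What the plan says.** Section 8.2 is worded as an obligation: "A subject will be withdrawn from the study for any of the following reasons". One listed reason is "Subject lost to follow-up, i.e. misses two consecutive follow-up questionnaires". Section 4.1 sets the questionnaires at "2-weeks (day 10-30), 4-months (day 110-150) and 12-months (day 345-395) from Visit 1".

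Section 2.2 makes these questionnaires the source of the outcomes: "All of the primary and secondary endpoints will be assessed using the follow-up questionnaire administered at 2-weeks, 4-months and 12-months after the enrollment visit". Section 14.3 states "Both primary and secondary analysis will be conducted on full analysis set" and defines that set as "All enrolled subjects (signed consent form) regardless of subsequent withdrawal from study or deviation from protocol", adding "At least one observation should be recorded". It does not say whether a Visit 1 record counts.

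In Section 7.2, step 4.1 sends the 12-month email and link to the registrant and states no exception for someone already withdrawn. Section 13 says that investigators do not report events of their own accord; events come to light through a question in the follow-up questionnaire. Section 14.9 does not impute missing values in the main analysis but plans multiple imputation as a sensitivity analysis.

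**The concern.** A lost-to-follow-up rule normally records that contact has failed. Here it can also end contact while one of three scheduled outcome assessments is still to come, for subjects who have not withdrawn consent. The 12-month assessment matters in its own right: it contributes to the overall odds ratio in the primary model (Section 14.5), and it is the lead time point of secondary hypothesis 1 (Section 2.3).

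Early non-responders may differ in satisfaction from those who answer. If so, ending their follow-up makes the 12-month data more selective, and no later analysis can recover a rating that was not collected. The same subjects have returned no adverse-event report, so the 12-month form is their only remaining planned route for one.

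**Working it through.** **1. When the rule acts.** With three questionnaires there are eight patterns of response (R) and miss (M), in the order 2-week, 4-month, 12-month. Three contain two consecutive misses:

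| Pattern absent the rule | Rule triggers | Effect on collection |
|---|---|---|
| R-M-M | day 395 | none; nothing remains to collect |
| M-M-M | day 150 | none in outcome |
| M-M-R | day 150 | becomes M-M-M; the 12-month rating is lost |

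The 12-month window opens at day 345, and 345 − 150 = 195 days after the trigger. The subject at stake is M-M-R, who has one follow-up rating if still asked and none if not.

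**2. Consequence for each analysis set.**
- If the observation required by Section 14.3 means a follow-up rating, the subject falls outside the full analysis set.
- If a Visit 1 record suffices, the subject stays in the set but has no outcome.
- Either way the primary model and the 12-month test receive nothing from this subject.
- Completer and per-protocol status do not change. Sections 8.1 and 14.3 require two questionnaires, and this subject could return only one.

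**3. The plan's sample size.** Section 14.2 uses N = [Zα√(2p̄q̄) + Zβ√(pCqC + pTqT)]² (1 + (n−1)ρ) / [n(pT − pC)²], with n = 3, two-sided α = 0.05 and 80% power. For 0.70 against 0.80 at ρ = 0.7: (1.960 × 0.6124 + 0.8416 × 0.6083)² × 2.4 / (3 × 0.01) = 2.9315 × 2.4 / 0.03 = 234.5, against 234 printed in Table 4. Thirteen of the 15 cells reproduce to rounding. The two exceptions are in the 0.77/0.86 row: 155.2 at ρ = 0.3 (145 printed) and 232.8 at ρ = 0.7 (242 printed). That is a separate matter, and this point does not rest on those cells. Enrolment reproduces: 240 / (1 − 0.20) = 300.

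**4. What continued collection could add to power (assumptions, not in the documents).** Suppose 2%, 5% or 10% of 300 per arm miss both early forms, and 25% to 75% of those would answer at month 12.
- 2%: 6 subjects, giving 1.5 to 4.5 extra ratings per arm.
- 5%: 15 subjects, giving 3.8 to 11.3.
- 10%: 30 subjects, giving 7.5 to 22.5.

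The baseline is 240 subjects with three ratings each, and each recovered rating counts as one effective observation. At ρ = 0.7 the effective number is 240 × 3 / (1 + 2 × 0.7) = 300 per arm. For 0.77 against 0.86, power is 81.2%, rising to 81.4% with 301.5 and 83.9% with 322.5. At ρ = 0.3 the effective number is 720 / 1.6 = 450, and power moves from 93.7% to at most 94.7%.

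**5. Incidence-rate denominator.** Section 14.6 counts days in study until the first event, dropout, death or study end. If dropout is dated to the close of the 4-month window, each such subject adds up to 150 / 365.25 = 0.41 patient-years with no event report ever returned. For the assumed 6, 15 or 30 subjects per arm this is about 2.5, 6.2 or 12.3 patient-years, beside roughly 240 from 240 completers followed for about a year. The plan does not say how dropout is dated, so this is an upper bound.

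**The case against.** The strongest reply is that little is lost. These subjects have ignored at least three emails at each of two time points, possibly with a text message as well, so many may not answer a third round. Enrolment already allows 20% dropout and rises if that is exceeded (Section 14.2), and a multiple-imputation sensitivity analysis is planned. This stands as to size: the effect on power is small. It does not justify giving up ratings that could be had, because neither provision collects one.

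Four stronger readings are tempting, and the documents do not support them.

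- *These subjects leave the full analysis set.* That depends on an undefined term. Section 14.3 keeps withdrawn subjects, and a Visit 1 questionnaire might satisfy its data requirement.
- *The 12-month rating is never sought.* This is an inference from withdrawal. No section says the email stops, and step 4.1 names no exception.
- *The rule erodes a thin sample-size margin.* The 240 target counts completers, and a subject who missed the first two forms can never be one.
- *The adverse-event criterion, "Subject develops significant or serious adverse events causing discontinuation of study lens wear", does comparable harm.* The rating items in Section 2.2 refer to the lenses being worn, so a subject who has stopped them may have nothing current to rate. The incidence rate is already censored at the first serious or significant ocular event. The questionnaire specifications in Appendix A are not visible, so how the forms treat such subjects cannot be judged.

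**Conclusion.** The concern holds in a narrow form. As written, Section 8.2 withdraws a consenting subject at about day 150 for missing two questionnaires, and nothing provides for collection afterwards. Step 4.1 of Section 7.2 can be read the other way, so the passages must be reconciled. If the withdrawal reading is followed, a subject who would have answered at month 12 contributes no outcome and no event report, while up to 150 days may still enter the incidence-rate denominator.

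Neither the number of such subjects nor the direction or size of any bias can be calculated from the documents. Under the assumed ranges power changes by less than 3 percentage points at ρ = 0.7 (81.2% to at most 83.9%) and by 1 point at ρ = 0.3. The reason to act is less selective 12-month data and better event capture. This is an inexpensive improvement and does not put the trial's main conclusion in doubt.

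**What to change.** - **Section 8.2:** declare loss to follow-up only after the 12-month window closes (day 395). State that the 12-month questionnaire and its reminders go to every subject who has not withdrawn consent, even if both earlier forms were missed. This brings 8.2 into line with step 4.1 of Section 7.2.
- **Section 14.3:** state that the required observation is at least one follow-up rating.
- **Section 14.6:** state the date on which exposure ends for a subject who never answers. Without this, moving the declaration to day 395 could put up to 395 unreported days per subject in the denominator instead of 150.
- Leave the adverse-event, non-compliance and investigator-judgment criteria in 8.2 as they are. The change concerns data collection only.

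The cost is protocol wording, some extra reminders from a system already in place, and a few more vouchers. Some subjects will have only a 12-month rating, which the mixed model can use. Under the clarified definition, consented subjects who never return a rating are outside the full analysis set, so their number should be reported by arm.
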